# PROTOCOL SUMMARY

Title:	Mesh Matters: Evaluating the Efficacy of Suture Mesh vs. Regular Mesh in Ventral Hernia Treatment – a randomized, blinded, multicenter study
Acronym:	MeMa
Study Sponsor:	[name]
Protocol version:	1.3 (07.07.2025)
Coordinating investigator:	[name]
Study sites:	a) Regionshospital Nordjylland, Hjørring b) Regionshospital Randers c) Regionshospitalet Viborg d) Regionshospital Horsens
Investigators and clinical study coordinators:	Coordinating investigator: [name]  Site investigators (according to above mentioned sites): a) [name], DMSc/[name] , MD b) [name] c) [name] d) [name], PhD
Other collaborators:	Center for Klinisk Forskning, Regionshospital Nordjylland Dansk Center for Sundhedstjenesteforskning, Aalborg Universitet.
Funding organizations	Investigator initiated. Funding will be sought from various non-profit foundations. As of now (July 7 th 2025) only internal funding from Regionshospital Nordjylland has been secured.
Indication:	Patients with small (< 3*3 cm) ventral hernia, with indication for onlay mesh repair.
Aim:	Superiority of mesh suture repair.

Hypothesis:	By using mesh suture, most of the subcutaneous dissection may be avoided and thus our hypothesis is that by reducing the surgical trauma, we may reduce wound complications from 14% to 4%, as well as reduce the operation time.
Study design:	Multicenter, blinded, randomized, controlled trial.
Planned sample size:	280 (140 in each arm)
Total number of centers:	4
Screening:	All patients presenting with small (< 3*3 cm) ventral hernia in the outpatient clinic.
Selection criteria:	Capable adults (age > 18 years) where indication for open surgery with onlay planar mesh is found.
Study interventions:	Mesh suture vs. planar mesh repair.
Primary outcome	Surgical site occurrences (SSOs)
Analysis plan:	No interim analysis is planned. Full analysis will thus be performed after inclusion of the planned sample size of 280 participants.
Duration of study:	Patient inclusion 1,5-2 years, 5 years follow up.

## INTRODUCTION

In this multi-center, blinded, randomized study, we compare two medical devices to treat small ventral hernias: Mesh suture (intervention) vs. planar mesh (standard treatment).

Implantation of mesh suture does not require the subcutaneous preparation of abdominal wall needed to implant planar mesh. Thus, we hypothesize that the reduced surgical trauma following mesh-suture implantation promotes better postoperative outcomes, primarily reduced wound complications such as seroma, hematoma and wound infections. Additionally, the shorter operation time associated with mesh-suture implantation may substantially reduce hernia waiting lists, which approximate 41 weeks in some public hospitals in Denmark. Finally, we will assess patient-reported outcomes (PROMs) such as Quality of Life (QoL) before and after surgery and analyze socio-economic parameters potentially affected by mesh-suture implantation, such as return to work and contact with family physician/primary sector.

# BACKGROUND

Surgery for small ventral hernias (< 2 cm) is one of the most frequently performed operations in Denmark, with 2469 procedures performed in 2023. Despite it being a relatively small operation, up to 7.1% of patients are readmitted to emergency departments <90 days after surgery, primarily due to wound problems, and up to 2.2% of patients are reoperated <30 days after surgery. Historically, the two most important outcome measures following small ventral hernia repair are postoperative wound events and long-term hernia recurrence. Current standard treatment of these hernias in Denmark is open surgery with onlay planar mesh placement. With onlay planar mesh, the hernia sack is dissected and reduced, the abdominal wall defect closed with a non-dissolvable suture, subcutaneous tissue dissected from the underlying fascia and non-resorbable mesh implanted on top of the fascia. This method is proven superior to closure of the hernia defect with only a suture in terms of recurrence rates. There is, however, a higher risk of seroma/hematoma formation and wound infection when planar mesh is used compared to suture closure. Rates of postoperative seroma formation are reported to be as high as 46% and in our clinical practice, readmission to hospital is predominantly caused by seroma formation related to the operative site.

Reported rates of surgical site occurrences (SSO) after operations for small ventral hernias vary greatly in the literature, additionally there is a lack of standardized definitions and reporting. In settings comparable to ours, one study from Sweden showed complication rates of 23.7% after onlay planar mesh repairs. The higher rate of hernia recurrence with suture only repair is attributed to the suture cutting through tissue (“cheese wire cutter effect/ or suture pull-through effect”), which occur when the sharp leading edge of the suture applies focused pressure at the suture/tissue interface and the pressure causes either abrupt cutting of tissue or a more gradual process of tissue ischemia and scarring, remodeling over time. In experimental studies, low suture tension has been found to promote more favorable collagen composition of the incisional region. Planar mesh implantation redistributes tension forces over a large surface area so the edges of fascia have optimal conditions for healing, but at the cost of higher wound complications rates and longer operation time.

Several methods have been developed to reduce fascial tension during healing without extensive dissection of suprafascial or subfascial tissue. Among those are mesh sutured repairs where 2 cm wide mesh strips are used to close fascial defects just as with single tread interrupted suture. Mesh sutured repairs showed promising results even in contaminated fields and larger defects. Mesh sutured technique is however subject to many variables that may alter its efficacy, such as accurate strip cutting, strip passing technique and mesh availability at the hospital.

Recently, a mesh suture has been developed (our proposed study intervention), with an attached needle and a tubular design with pores in the wall, combining functions of both suture and mesh, allowing ingrowth of tissue without capsule formation, while having the tensile strength nearly identical to those of a 0-

polypropylene suture. Available data support the safety and efficacy of this mesh suture for abdominal wall closure.

[figure not shown]
## AIM/PURPOSE

The aim of this randomized, blinded multicenter trial is to investigate differences in wound complication rates (SSO), PROM (Quality of Life) and operation time among patients operated for small ventral hernias either with mesh-suture or planar mesh as well as evaluate potential influence of mesh-suture on wider socio-economic parameters such return to work and contact with family physician/primary sector.

## HYPOTHESIS

By using mesh suture, extensive subcutaneous dissection is avoided and surgical trauma is minimized, leading to reduced wound complication rates.

## MEDICAL DEVICE

In this head-to-head study we intend to compare two medical devices. Both devices are used under the respective CE approved indications.

In **the control group** we use Optilene® Mesh. Manufacturer: B. Braun Surgical, S.A. [name]. CE Certificate G1 025701 0090 Rev.01.

Optilene® Mesh is a mesh implant for reinforcement of connective tissue structures. It is constructed from monofilament polypropylene, knitted to a thin and elastic shape-stable mesh. After implantation, the Optilene® Mesh adapts to the longitudinal and latitudinal expansions taking place in the connective tissue. Optilene® Mesh is coloured blue with copper phthalocyanine (Phthalocyaninato (2-) copper) for a better visibility. Optilene® Mesh does not possess any independent pharmacological properties. The polypropylene mesh is biostable and is not degraded in the body.

In **the intervention group** we use suturable mesh, DURAMESH™. Manufacturer: Mesh Suture Inc. [name]. Authorized representative: Emergo Europe, [name]. CE Certificate US21/819944390

DURAMESH™ is a non-absorbable polypropylene suturable mesh and combines the desirable principles of a mesh repair with the placement precision of a suture. DURAMESH™ distributes forces at the suture-tissue

interface, while dramatically minimizing the amount of implanted foreign material and surgical complexity required for implantation. DURAMESH™ is constructed from monofilament polypropylene and has an open walled, hollow core design that allows fibrovascular incorporation into the device during healing. DURAMESH™ does not possess any independent pharmacological properties. The polypropylene suturable mesh is biostable and is not degraded in the body.

## METHOD

### Study design

Multicenter, blinded, randomized controlled trial. The study is powered as a superiority study with intention to treat analysis.

### Study population and sample size

In the literature, wound complication incidences vary greatly (from 0.7 to 63.3%), at least in part due to a lack of standardized definitions and reporting. We know that in our department the readmission rate after small ventral hernia repair is 7% (data from the National Hernia Database, 2023). The majority of these readmissions is due to wound complications. We estimate that least as many patients are treated for minor SSO in primary sector as in the hospitals (unpublished data), so the true incidence of wound complications is estimated around 14 percent for onlay mesh.

In the literature the reported *surgical site event* rate for umbilical hernias is 2.4%, with infection rates of 4.9%. For ventral hernias, surgical site events range from 1% to 8.2%, while infections range from 3.1% to 5.2%.

It is also important to note the *wound classification* in the referenced study:

- **Umbilical hernias:** 14.6% were classified as *clean-contaminated*
- **Ventral hernias:** 18.6% *clean-contaminated* and 12.4% *contaminated*

In our study, all procedures are performed in an **outpatient setting** and involve only **clean wounds**.

Additionally, **13% of patients** in the referenced cohort were **active smokers**, despite smoking being a well-established risk factor for postoperative wound complications. In our study, the rate of active smoking is **0%**, as all participants are required to be smoke-free for at least **six weeks preoperatively**, with random testing performed to verify compliance.

Based on these distinctions, our *realistic* expectation for wound complications is **1–3%**. However, to remain appropriately conservative, we have chosen to report an estimated complication rate of **4%**.

A reduction in wound complications from 14% to 4% is considered clinically significant.

A sample size of 254 participants was determined to have 80% power to detect a clinically significant between-group reduction in surgical site occurrences (seroma/hematoma formations and postoperative wound infections) from 14 to 4% and a type I error of 5%, without increase in recurrences. This number was increased to 280 participants to account for conversions and cases lost to follow-up.

No interim analyses are planned. The planned sample size is 280 patients with equal assignment to the two groups.

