## **Safety assessment and study termination**

Conversion of intervention to standard treatment: If, after randomization, interventional treatment is impossible to apply, then standard treatment will be performed.

The study will be terminated if the complication rate for patients operated with mesh suture exceeds known complication rates for planar mesh. Adverse events will be assessed and registered 7-13 days after surgery by clinical examination and 90 days after surgery by phone as well as by going through patient medical records.

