## **Statistical methods**

A sample size of 254 participants was determined to have 80% power to detect a clinically significant between-group reduction in surgical site occurrences from 14 to 4% and a type I error of 5%. This number was increased to 280 participants to account for conversions and cases lost to follow-up. No interim analyses are planned.

Data will be analyzed by a blinded analyst on an intention-to-treat basis, according to the prespecified statistical plan. A two-sided P-value  $< 0.05$  is considered significant.

Analysis of the primary outcomes: Depending on the distribution of data, continuous variables will be described with mean (SD, standard deviation) or median [interquartile range (IQR)] and analyzed with students t-test or Mann-Whitney U test, respectively. Categorical variables will be described as frequencies (%) and analyzed using Fisher's exact test.

Analyses will be conducted using Stata software.

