## APPENDIX 1:

### Definition of SSO:

The standardized definition for surgical site infection (SSI) as defined by the Centers for Disease Control and Prevention (CDC): An infection that occurs in the part of the body where the surgery took place and includes superficial, deep, and organ space SSIs.

The standardized definition for SSO as defined by the VHWG includes any SSI as well as wound cellulitis, non-healing incisional wound, fascial disruption, skin or soft tissue ischemia, skin or soft tissue necrosis, wound serous or purulent drainage, stitch abscess, seroma, hematoma, infected or exposed mesh, or development of an enterocutaneous fistula. All complications will furthermore be classified according to the Clavien-Dindo classification system.

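### Conversions share one head-count allowance with losses although under intention-to-treat they dilute the effect; 280 leaves almost no reserve under Fisher's exact test, and the umbilical figures do not support calling 4% conservative

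*Protocol*

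**What the plan says.** The protocol's section on study population and sample size sets the planar-mesh rate by a departmental estimate: "so the true incidence of wound complications is estimated around 14 percent for onlay mesh". The target difference is explicit: "A reduction in wound complications from 14% to 4% is considered clinically significant".

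For mesh suture it cites one source. In umbilical hernias the surgical site event "rate for umbilical hernias is 2.4%, with infection rates of 4.9" per cent. For the wider group: "For ventral hernias, surgical site events range from 1% to 8.2%, while infections range from 3.1% to 5.2" per cent. It then notes that the source included wounds that were not clean and 13% active smokers, states a realistic expectation of 1–3%, and continues: "However, to remain appropriately conservative, we have chosen to report an estimated complication rate of" 4%.

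Appendix 1 defines the primary outcome, SSO, as a composite that "includes any SSI as well as wound cellulitis", seroma, hematoma and other wound events.

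The sample size is 254 for 80% power and a 5% type I error. The Statistical methods section adds: "This number was increased to 280 participants to account for conversions and cases lost to follow-up". No split between the two causes and no rate for either is given. The analysis is by intention to treat, with a two-sided 5% level and Fisher's exact test for categorical variables. The section on safety assessment and study termination gives the direction of conversion: "If, after randomization, interventional treatment is impossible to apply, then standard treatment will be performed".

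**The concern.** Two planning inputs look more favourable than the protocol's own text allows.

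The first is the allowance for conversions. Loss to follow-up removes a patient from the analysis, and a head-count increase repairs that. Conversion under intention-to-treat removes nobody. It leaves in the mesh-suture arm a patient who received planar mesh, so the difference between the arms shrinks. A shrinking difference costs more patients than the same share of losses, so one shared allowance of 26 cannot be read as covering both.

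The second is the word conservative. Infection is one component of SSO, so an SSO rate cannot be lower than the infection rate in the same patients. The planned 4% for the whole composite is lower than the 4.9% cited for infection alone in umbilical hernias.

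At stake is the stated 80% power. If it is taken at face value, a non-significant result could be reported as coming from an adequately powered trial when the power under the planned test was lower.

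**Working it through.** **Inputs (all from the protocol).** Planar mesh 14%, mesh suture 4%, 1:1 allocation, two-sided 5%, 80% power, 254 raised to 280, Fisher's exact test, intention to treat. The conversion share c and the loss rate are not given. The values below are assumptions.

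**1. Reproduce 254.** The protocol names no formula. The pooled normal approximation without continuity correction is

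n per arm = [1.96·√(2·p̄(1−p̄)) + 0.842·√(p₁(1−p₁) + p₂(1−p₂))]² / (p₁−p₂)², with p₁ = 0.14, p₂ = 0.04, p̄ = 0.09.

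This gives 127.4. Rounded up, that is 128 per arm or 256 in total, within two patients of the stated 254, and power at 127 per arm is 79.9%. So 254 is correct for that formula. The step to 280 adds 26 patients (26/280 = 9.3%), and 254 × 1.10 = 279.4 also leads to 280.

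**2. Apply the planned test.** Power of Fisher's exact test, by enumerating all outcomes of two binomials at 14% and 4%:
- 127 per arm (254): 75.2%
- 140 per arm (280): 80.4%

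Under the planned test the 26 extra patients are therefore used up in reaching 80%, and almost nothing is left for conversions or losses.

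**3. Put conversions where intention-to-treat puts them.** If converted patients carry the planar-mesh rate, the mesh-suture arm's rate is

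(1−c) × 4% + c × 14% = 4% + 10 points × c.

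So c = 2% gives 4.2%, c = 5% gives 4.5% and c = 10% gives 5.0%. Power against 14%, by enumeration, with the uncorrected chi-square test for comparison:

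| Converted (assumed) | Arm rate | Analysed per arm | Fisher | Chi-square |
|---|---|---|---|---|
| 0% | 4.0% | 140 | 80.4% | 85% |
| 2% | 4.2% | 140 | 78% | 83% |
| 5% | 4.5% | 140 | 74% | 80% |
| 10% | 5.0% | 140 | 68% | 74% |
| 5%, and 5% lost | 4.5% | 133 | 71.5% | 79% |
| 10%, and 5% lost | 5.0% | 133 | 65% | 73% |

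(140 × 0.95 = 133.)

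**4. What the 26 patients buy on the protocol's own kind of formula.** With the pooled formula of step 1 and no losses at all, 80% power needs 270 patients at c = 2%, 290 at c = 5% and 332 at c = 10%. If the whole 9.3% allowance were conversions, the arm rate would be 4.93% and the requirement 326. So even by that formula 280 covers conversion only up to a share between 2% and 5%, and only if nobody is lost.

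**5. Set 4% against the cited rates.**
- Umbilical: infections are 4.9% and site events 2.4%. Since 4.9 exceeds 2.4, the site-event figure cannot contain all the infections. SSO in that source is at least 4.9%, and 2.4 + 4.9 = 7.3% if the two do not overlap at all.
- Ventral: infections are 3.1–5.2% and site events 1–8.2%. The planned 4% lies inside both ranges.

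At 4.9% for mesh suture, 140 per arm give 69% power (Fisher) or 75% (chi-square).

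**6. How large a discount does 4% need?** Suppose the cited clean-contaminated cases (14.6%) and smokers (13%) do not overlap, so together they are 27.6% of the source, and the overall rate is 4.9%. For the other 72.4% to be at 4%, the 27.6% would need (4.9 − 4 × 0.724)/0.276 = 7.3%. For the others to be at 3%, it would need (4.9 − 3 × 0.724)/0.276 = 9.9%. The protocol shows no such calculation.

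**The case against.** The strongest reply on the 4% is that conservative refers to the protocol's own expectation of 1–3%, stated immediately before, and that reasons are given: clean wounds, an outpatient setting, no active smokers. Relative to that expectation 4% is cautious, and at a true 3% power with 140 per arm is about 90% (Fisher). Step 6 also shows that 4% does not need an extreme discount from 4.9%. This stands. What remains is that the discount is asserted without a figure, and that the clean-wound and smoke-free conditions it relies on are not in the listed inclusion and exclusion criteria (the separate guideline file of Appendix 2 is not at hand).

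A reader might go further and infer that the comparable SSO rate is 4.9–7.3%, that 80% power holds only in the best case, and that a halving of SSOs would probably be missed. The documents do not support this. The 7.3% assumes no overlap between the two umbilical figures. The source's denominators, definitions and follow-up window are not given, while this trial counts SSOs at day 7–13. The ventral ranges include 4%. Raising only the mesh-suture rate is also one-sided, since the Background cites 23.7% after onlay mesh in a comparable setting. And the declared target is 14% to 4%, so low power for a halving is not in itself a defect.

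On conversions, the reply is that the protocol never says converted patients are removed, that raising the sample size is a legitimate way to offset dilution, and that randomization takes place during surgery after unsuitable defects are ruled out, so conversions should be rare. The last point stands and limits the size of the problem. The others do not resolve it: with no rate and no split, nobody can tell how much dilution the 26 patients were meant to absorb, and under Fisher's test even 2% conversion without losses gives 78%.

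**Conclusion.** The conversion point holds. The protocol combines dilution and loss in one head-count allowance, and under its planned test 280 patients reach the stated 80% with virtually no margin (80.4% with no conversion and no loss). The shortfall is small if conversions are as rare as intraoperative randomization suggests (78% at 2%) and material if they are not (68% at 10%, or 65% with 5% also lost). These figures assume that converted patients carry the 14% rate, and the conversion and loss rates are illustrations that do not come from the protocol. With a chi-square test, power stays at about 80% or above up to 5% conversion without losses.

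The point on the 4% holds in a limited form. It is below the cited umbilical infection rate but not below every cited infection rate, so it is unsupported as conservative against the umbilical figures and is not shown to be wrong. The sample size arithmetic behind 254 is sound.

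**What to change.** Keep the sample size at 280. In the sections on sample size and on statistical methods:

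- Treat conversions as dilution, with the mesh-suture rate written as 4% + 10 points × c and an assumed c stated. Note that randomization after inspection of the defect should keep c low.
- Treat losses as a reduction in the number analysed, with their own assumed rate. The split of the 26 extra patients is for the sponsor to state, because the protocol does not give it.
- Restate the power at 280 under Fisher's exact test on that basis, and add one sensitivity value at a mesh-suture rate of 4.9% (69% Fisher, 75% chi-square, no losses).
- Describe 4% as above the protocol's own 1–3% expectation, and drop the claim that it is appropriately conservative.

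The cost is a few sentences and one short table, and a stated power less favourable than the present one. No procedure, visit or patient number changes.

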## **Inclusion criteria**

All patients presenting with small ventral hernia, maximum 3x3cm, where indication for open surgery with planar mesh is found.

## **Exclusion criteria**

Age <18 years

Acute operation

Pregnancy

Women with plans of future pregnancies

Withdrawal of informed consent during admission

## **Recruitment of study subjects**

Patients are screened at the participating centers outpatient departments. If the candidate meets the inclusion criteria, the candidate will receive oral and written information about the study from one of the operating surgeons. Patients will be asked to read the information in the entity before signing. All patients are invited to discuss the entry into the study with a relative or other entrusted person if they so choose. Informed consent will take place in a quiet room without interruption on the day of the inclusion. Patients are informed that the consent could be withdrawn at any time prior to randomization (or after) and so the real timeframe to decide if patients wish to participate would be approximately 4 weeks.

